4.6.2 Injection Site Evaluations

Injection site evaluations will be performed according to the SOA ([Table 1-1](#), [Table 1-2](#), [Table 1-3](#), and [Table 2](#)) and will be summarized by visit according to severity (none, mild, moderate, severe) and type of reaction (erythema, edema, induration, itching, pain or tenderness, or other reaction). For patients reporting more than one occurrence of the same type of reaction, the most severe reaction will be used for the summary.

A by-patient listing will be provided for all injection site evaluations and will also include measurement (if applicable).

4.6.3 Laboratory Data

Clinical laboratory values will be using the International System of Units (SI).

The actual value and change from baseline to each on-study evaluation will be summarized for each clinical laboratory parameter by visit.

In the event of repeat values, the last non-missing value per study day/time will be used.

The frequency of patients with abnormal safety laboratory results will be tabulated. Shift tables of change in CTCAE grade of laboratory parameters from baseline by visit will be presented for hematology and clinical chemistry by RGDO and overall, if applicable.

All laboratory data, including pregnancy test results, will be provided in data listings.

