## 11.18. Safety Laboratory Tests

Clinical safety laboratory tests will be performed by a central laboratory. Blood and urine samples are to be collected following an 8-hour fast and prior to dosing, according to the SOA (Table 3).

All clinically significant laboratory abnormalities will be followed-up by repeat testing and further investigated per the judgment of the Investigator.

Specific tests are described below.

In certain situations, it may not be feasible to complete all blood draws scheduled for a specific visit (e.g., a younger patient, or difficulty with phlebotomy due to obesity). In this situation, the Investigator may use his/her discretion to determine which laboratory tests are completed. Laboratory tests should be prioritized in the following manner:

1. Safety labs; including hematology, chemistry, and coagulation profile.

3. All other laboratory measures, such as

Any patient who does not complete all blood draws as described in the SOA on two visits should be discussed with the Sponsor.

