3.11. Visit Windows

It is expected that all visits should occur according to the protocol schedule. For patients enrolled prior to amendment 9, visits should start to transition towards the post-amendment 9 SOA as outlined in [Section 1.3.1](#). All data will be tabulated per the evaluation visit as recorded on the CRF even if the assessment is outside of the visit window. If the evaluation visit is missing in the database but there are data from an unscheduled or additional visit that is inside the visit window, the data from the unscheduled or additional visit will be used in data summaries. If a patient discontinues or completes the study prior to having their visits updated to align with the post-amendment 9 schedule of assessments, then the patient's visits will be mapped in accordance with the amendment 9 schedule of assessments as outlined in a separate document. All available data will be listed for each patient.

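### Laboratory grade shifts are planned by visit only, so an abnormal value superseded by a same-day repeat, or found at most unscheduled draws, appears in no shift table

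*SAP*

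**What the plan says.** SAP section 4.6.3 sets one rule for repeats across the whole laboratory section: "In the event of repeat values, the last non-missing value per study day/time will be used". It plans three tabulations: actual value and change from baseline by visit; an abnormality count ("The frequency of patients with abnormal safety laboratory results will be tabulated"); and grade shifts ("Shift tables of change in CTCAE grade of laboratory parameters from baseline by visit will be presented for hematology and clinical chemistry", by RGDO and, where applicable, overall). It also plans that "All laboratory data, including pregnancy test results, will be provided in data listings". It names no shift to the worst post-baseline grade.

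SAP section 3.11 decides which samples belong to a visit. The default is that "All data will be tabulated per the evaluation visit as recorded on the CRF even if the assessment is outside of the visit window". An unscheduled sample is used only as a substitute: "If the evaluation visit is missing in the database but there are data from an unscheduled or additional visit that is inside the visit window", it enters the summaries. No other route is given.

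Protocol section 11.18 says which values are repeated: "All clinically significant laboratory abnormalities will be followed-up by repeat testing". It does not say when the retest is to be drawn.

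**The concern.** Taking the last of several repeats is a reasonable way to get one value per patient per visit for a mean. It is a poor way to describe how severe abnormalities became. The protocol requires repeats after clinically significant abnormalities, so the replaced values come disproportionately from that group, and a transient abnormality is likely to look better on repeat.

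Unscheduled draws raise the same problem. Post-amendment 9 laboratory visits are four weeks apart on treatment, and bridging visits are up to 12 weeks apart. An abnormality that arises and resolves between visits will mostly be seen only at an unscheduled sample.

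Laboratory evaluations are part of the safety secondary endpoint, and the shift tables are the only planned summary of laboratory grade that does not depend on an investigator's view of clinical relevance. Groups are small: the protocol expects 1 to 15 patients per subgroup, and the SAP at least 5. One patient missing from a table is 1/5 = 20 percentage points in a group of 5 and 1/15 = 6.7 points in a group of 15.

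**Working it through.** The documents give no figure on this point, so there is none to reproduce. Two checks were made.

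**1. How much of the study lies inside a laboratory window**

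Inputs, from the post-amendment 9 Schedule of Assessments (SAP Table 2; Protocol Table 3): post-baseline safety laboratory draws on Days 29, 57, 85, 113 and 141, each ±3 days.

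- Days covered: 5 visits × 7 days = 35.
- Days from Day 2 to the end of the last window (141 + 3 = 144): 144 − 2 + 1 = 143.
- Days outside every window: 143 − 35 = 108, and 108/143 = 76%.
- For a patient who moves to the extension study at Visit 6, the span is Day 2 to Day 116, or 115 days, with 4 × 7 = 28 covered: 115 − 28 = 87, and 87/115 = 76%.

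On those days an unscheduled sample cannot enter a by-visit table even as a substitute. On the remaining 35 days it enters only if the scheduled evaluation is missing. Bridging visits are not counted.

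**2. The written rules applied to five hypothetical patients**

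Each patient has one Grade 3 value and is otherwise Grade 0. The rules of SAP sections 4.6.3 and 3.11 are applied as written, reading the repeat rule as one value per study day.

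| Case | Where the Grade 3 value arises | Highest grade in any by-visit shift | Highest grade observed |
|---|---|---|---|
| A | Day 57 visit; Grade 0 on a same-day repeat | 0 | 3 |
| B | Day 57 visit; Grade 0 on a retest on Day 64 | 3 | 3 |
| C | Unscheduled, Day 70, between visits | 0 | 3 |
| D | Unscheduled, Day 58; Day 57 evaluation missing | 3 | 3 |
| E | Unscheduled, Day 58; Day 57 value present and Grade 0 | 0 | 3 |

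The by-visit rule shows Grade 3 in 2 of 5 cases (B and D). A worst-post-baseline shift over all samples shows it in 5 of 5. The cases show which routes lose a value. They are not a sample, and 2 of 5 is not an estimated rate.

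**What the rules leave undefined**

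- If a site records two draws from different days under one CRF visit, no rule says which is tabulated.
- The abnormality count is not stated to be by visit, and the SAP does not say whether unscheduled or superseded values count towards it.

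**The case against.** The strongest reply is that little is lost in practice. It has five parts.

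- **Retests usually come later.** Safety samples go to a central laboratory and are drawn fasted and before dosing (Protocol 11.18), so a retest prompted by a reported result will usually fall on another day. The repeat rule works per study day/time, so the triggering value then stays at its visit, as in case B. This stands. A reader might infer that repeat testing generally erases the abnormal result that prompted it; the documents support that only for a same-day repeat.
- **Unscheduled data are not shut out.** A reader might infer that only scheduled visits are tabulated. SAP section 3.11 does admit an in-window draw when the scheduled evaluation is missing. This stands too, but the exception is narrow.
- **The values are reported elsewhere.** All laboratory data are listed, and with so few patients the listings can be read. Protocol section 12.2 makes clinically relevant laboratory deterioration an adverse event, and SAP section 4.6.1 counts each patient once, at the most intense or most related occurrence. This softens the consequence. But a listing is not a tabulated grade, and the adverse event route depends on judged relevance.
- **The last-value rule is not one-directional.** A repeat that is worse is also kept. This is correct: the pull towards normal is a tendency that comes from which values are repeated.
- **The study is exploratory and uncontrolled.** This limits the weight of the point but does not favour the present rule. The SAP's other safety summaries go the other way: the most intense adverse event (4.6.1) and the most severe injection site reaction (4.6.2). Protocol section 13.4 plans change from baseline to any post-dose value and keeps out-of-window data in endpoint analyses. SAP section 1.1.1 lets the SAP supersede the protocol, but section 4.6.3 does not say that it is narrowing that plan.

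**Conclusion.** The concern holds for the grade-shift tables. As written, they omit a value superseded by a same-day repeat, every unscheduled value drawn outside a window, and every in-window unscheduled value where the scheduled one exists. For the abnormal-result frequency table the finding is a gap, not an error: its input is undefined.

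The firm figure is 108 of 143 days (76%) outside every post-amendment 9 laboratory window. It is a share of calendar days. To say that most unscheduled draws are lost assumes that they are not concentrated around visits and are not recorded under a scheduled visit label. The same-day finding assumes that the repeat rule is applied per day; the day/time wording leaves room for another reading.

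The documents give neither the frequency of same-day retests nor the number of unscheduled draws, so no rate of missed patients can be calculated. A reader might also infer that such values vanish from the report. They do not, because listings and adverse event tables remain. The change should be made because it is cheap and restores a grade summary free of investigator judgement. It does not bear on the primary endpoint.

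**What to change.** In SAP section 4.6.3:

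1. Limit the last-value rule to the by-visit summaries of actual value and change from baseline.
2. Add to each CTCAE shift table a column for the worst post-baseline grade, taken over all scheduled, repeat and unscheduled post-baseline samples except those the laboratory flagged as invalid.
3. State that the abnormal-result frequency table uses the same set of values, with each patient counted once.
4. State in section 3.11 that the substitution rule for unscheduled visits governs by-visit summaries and does not restrict items 2 and 3.

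No new data are needed. The cost is a few sentences, one column per shift table and slightly less favourable abnormality rates. Patients sampled more often also have more chances of an abnormal value, so the by-visit columns should stay alongside the new one.

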4.6.4 Vital Signs

Vital signs will be measured according to the SOA ([Table 1-1](#), [Table 1-2](#), [Table 1-3](#), and [Table 2](#)). Aside from those used in efficacy evaluations, the actual value and change from baseline of additional vital signs of temperature, heart rate (HR), mean systolic blood pressure (BP), mean diastolic BP, and respiratory rate will be summarized descriptively by visit. A by-patient listing of all vital signs will be provided.

4.6.5 Physical Examination and Comprehensive Skin Examination

Physical exams will be performed according to the SOA ([Table 1-1](#), [Table 1-2](#), [Table 1-3](#), and [Table 2](#)). A by-patient listing of all physical exam findings will be provided; results of the comprehensive skin examination will be provided in a listing.

Fitzpatrick classification data will be provided in a by-patient listing as available.

4.6.6 12-Lead Electrocardiogram

Electrocardiogram (ECG) results will be measured as shown in the SOA ([Table 1-1](#), [Table 1-2](#), [Table 1-3](#), and [Table 2](#)) and will be summarized with descriptive statistics and in a by-visit shift table, including the number and percentage of patients with normal results, non-clinically significant abnormal results, and clinically significant abnormal results at baseline and shift to each study visit.

ECG data for each patient, including HR, PR interval, QRS duration, QT interval, and QT interval corrected with Fridericia's method, as well as the overall interpretation will be provided in a data listing.

4.6.9 Prior and Concomitant Medications

Prior and concomitant medications will be assessed according to the schedule in [Table 1-1](#), [Table 1-2](#), [Table 1-3](#), and [Table 2](#) and coded using the WHO Drug Dictionary. The use of prior and concomitant medications will be included in separate summary tables by subgroup of RGDO and overall. Medications will be tabulated by Anatomical Therapeutic Chemical class and Preferred Term. Prior and concomitant medications will also be included in a by-patient data listing.

4.6.10 Anti-RM-493 Antibody Measurements

Blood samples for Anti-RM-493 antibody assessment will be collected as shown in the SOA ([Table 1-1](#), [Table 1-2](#), [Table 1-3](#), and [Table 2](#)). Results will be provided in a by-patient listing, including the date of the assessment and result, based on the availability of ADA data.

[REDACTED]

[REDACTED]

[REDACTED]

[REDACTED]

